3. STUDY DESIGN

3.1. General Study Design

This is a Phase III, randomized, double-masked, active-controlled, parallel-group, multi-center study. Subjects diagnosed with glaucoma or OHT who meet eligibility criteria at Visit 1 (Screening) will discontinue their current topical IOP-lowering medication(s), if any. After completing the required washout period, subjects will return for Visit 2 (Baseline, Day 1). Subjects who meet all eligibility criteria at baseline will be randomized to receive double-masked treatment for 3 months (Figure 1).

Approximately 400 eligible adults and up to 30 eligible pediatric subjects with glaucoma or OHT were planned to be randomized. At the time of finalizing this SAP, enrollment for this study had completed and no pediatric subjects were randomized in this study. Thus, only analyses regarding adult subjects are presented in this SAP.

Figure 1: Study Design Diagram

3.2. Randomization and Masking

A blocked randomization stratified by age (< 18 and ≥ 18 years old) will be employed to randomize eligible subjects in a 1:1 ratio to receive either DE-117 or Timolol. The randomization schedule will be generated and implemented by an independent CRO, Medidata Solutions, Inc. (New York City, NY).

This is a double-masked study. The subjects, Investigators, Examiners, and Santen personnel involved in the conduct of the study will be masked to the study treatment. An authorized unmasked study staff member who is not the Investigator or Examiner at the investigative site

will dispense and collect study medication(s) and will query about dosing compliance. In case of a medical emergency, when the unmasking of a subject's treatment assignment code becomes necessary for the welfare of that subject, the Clinical Investigator may reveal the treatment information by unmasking which treatment the subject has received through the study's interactive web response system (Medidata RTSM).

3.3. Sample Size Planning

The sample size calculation was based on a two-sided Type I error rate of 5% and a non-inferiority margin of 1.5 mmHg. Assuming a treatment difference of 0 mmHg between the DE-117 arm and the Timolol arm, a standard deviation (SD) of 4.0 mmHg, and a correlation coefficient of 0.6 among repeated measures, approximately 400 adult subjects in total (200 subjects per treatment arm) will provide 90% power to demonstrate non-inferiority of DE-117 Ophthalmic Solution 0.002% to Timolol Maleate Ophthalmic Solution 0.5% in IOP-lowering effect.

The standard deviation of 4.0 mmHg was determined from previous DE-117 studies conducted in the United States: 33-002 and 33-003.

3.4. Visits and Assessments

There are 5 scheduled visits for each subject. Assessments at each visit and the time/visit window for each post-baseline assessment are specified in the Assessment Schedule for Adult ([Table 1](#)). If the study drug administration is discontinued prior to Visit 5, the subject should be encouraged to still participate in follow-up study visits until Visit 5 on an observational basis. For subjects whose study participation is terminated prior to Visit 5 (Month 3), to the extent possible, all assessments scheduled for Visit 5 (Month 3) will be performed at the Exit Visit.

Table 1: Assessment Schedule for ADULT Subjects

	Washout Period		Double-Masked Treatment Period			
	Visit 1 Screening	Washout Period (up to 4 weeks) Optional Visit 1a	Visit 2 Eligibility/Baseline (Day 1)	Visit 3 Week 1 (Day 8±2)	Visit 4 Week 6 (Day 43 ±3)	Visit 5 Month 3 (Day 91±7) Exit or Early Termination ⁿ
Informed Consent(s) including the optional consent for pharmacogenomics/ genomics laboratory research study ^a	X					
Inclusion/Exclusion Criteria	X		X			
Demographics and Medical History, including prior PGA ^b	X					
Concomitant Medications/ Therapies	X	X	X	X	X	X
Dosing Compliance				X	X	X
AEs		X	X	X	X	X
Pregnancy Test ^c	X		X			X
Vital Signs (blood pressure/pulse rate) ^d	X		X (08:00)			X (08:00)
Refraction ^e	X					
BCVA ^e	X	X	X (08:00)	X (08:00)	X (08:00)	X (08:00)
Biomicroscopy ^f	X	X	X (08:00)	X (08:00)	X (08:00)	X (08:00)
IOP ^g	X	X	08:00 10:00 16:00	08:00 10:00 16:00	08:00 10:00 16:00	08:00 10:00 16:00
Pachymetry ^h	X					
Instill study medication after IOP measurement				X (08:00)	X (08:00)	X (08:00)
Iris color, eyelash, eyelid ⁱ			X (photo)			X (photo)
Gonioscopy ^j	X					
Visual Field ^k	X					
Ophthalmoscopy ^l	X (pupil dilation)		X (16:00)			X (16:00, pupil dilation)
Blood Sampling for Pharmacogenomics/genomics ^m				X		

Table 1: Assessment Schedule for ADULT Subjects (Continued)

	Washout Period		Double-Masked Treatment Period			
	Visit 1 Screening	Washout Period (up to 4 weeks) Optional Visit 1a	Visit 2 Eligibility/Baseline (Day 1)	Visit 3 Week 1 (Day 8±2)	Visit 4 Week 6 (Day 43±3)	Visit 5 Month 3 (Day 91±7) Exit or Early Termination ⁿ
Dispense Study Medication			X		X	
Collect Study Medication					X	X
Phone call to remind subject to take evening dose on the day before each visit				X	X	X

^a Informed Consent Form must be signed and dated before study procedures are performed. Informed consent for the optional pharmacogenomics/genomics laboratory research study may be obtained at any visit prior to study exit.

^b Prostaglandin naive subjects are defined as subjects who are not known to have used prostaglandin as their glaucoma treatment. The previous use of prostaglandin should be confirmed by either subject's medical records or subject history.

^c A urine pregnancy test will be conducted for all female subjects of childbearing potential.

^d Vital signs (resting blood pressure and pulse rate) will be collected in sitting position anytime at Visit 1 (Screening), and approximately 08:00 for Visit 2 (Baseline), and Visit 5 before the morning dose.

^e Refraction will be performed at the screening visit. If more than 10 letters in BCVA are lost compared to the screening visit, then refraction should be performed again. BCVA examination will be completed before IOP measurement at 08:00.

^f Biomicroscopy examination must be completed before IOP is measured at 08:00. Aqueous flare and cell evaluation will be performed before fluorescein instillation.

^g IOP measurements will be performed at 08:00, 10:00, and 16:00 (±60 min) at all visits except for Visit 1 and the optional Visit 1a (screening and mid-washout).

^h Pachymetry will be performed after IOP measurement at Visit 1 (Screening).

ⁱ Eye photograph will be taken at Visits 2 (Baseline) and 5 (Month 3).

^j If gonioscopy was performed within 3 months (90 days) prior to screening and was documented in the subject's records, no additional screening gonioscopy examination is necessary. Gonioscopy will be performed after IOP measurement at Visit 1 (Screening).

^k If visual field test was performed within 3 months (90 days) prior to screening and was documented in the subject's records, no additional screening visual field test is necessary.

^l Ophthalmoscopy will be performed at Visits 1, 2, and 5 (i.e. Screening, Baseline and Month 3) after the 16:00 IOP measurements. Ophthalmoscopy will be performed with pupil dilation at Visit 1 and Visit 5/exit or early termination. Dilation of the pupil will be performed after the 16:00 IOP measurement.

^m Blood sampling for the pharmacogenomics/genomics laboratory research study may be performed at any visit after pharmacogenomics/genomics informed consent obtained, subject randomized, and study drug dosing has begun.

ⁿ Optional at unscheduled visit, required for early terminated subjects.

4. DEFINITIONS

4.1. Time-Related Terms

4.1.1. Baseline Visit

The *Baseline Visit* is Visit 2 (Day 1) when the subject is randomized.

4.1.2. Treatment Start Date

Treatment start date is the date at which a randomized subject takes the first dose of the study medication.

4.1.3. Treatment End Date

Treatment end date is the date at which a randomized subject takes the last dose of the study medication. If the date of the last dose is missing, then

- The day before the Visit 5 (Month 3) date will be considered the treatment end date for subjects who completed the study.
- The day before the Exit Visit date will be used for subjects who prematurely discontinued from the study. If the Exit Visit date of a non-completer is not available, then the day before the last available visit date will be considered the treatment end date.

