#### **Double-Masked Treatment Period (3 months):**

Approximately 400 eligible adult subjects and up to 30 pediatric subjects will be randomized to receive either DE-117 0.002% QD in the evening and vehicle QD in the morning or Timolol Maleate 0.5% BID in a 1:1 ratio. Subjects will be treated for 3 months with scheduled visits at Visits 2, 3, 4 and 5 (Baseline, Week 1, Week 6 and Month 3).

At Visit 2 (Baseline), subjects will receive their first dose of study medication (study eye drops) as per their assigned/randomized study treatment at 20:00 ( $\pm 60$  min). The next day, subjects will subsequently dose with their assigned study medication at 08:00 ( $\pm 60$  min), and 20:00 ( $\pm 60$  min). At each scheduled follow-up visit, subjects will receive their morning dose of study medication/eye drops following the 08:00 IOP measurement at the investigative site (the doctor's office).

Timolol Maleate Ophthalmic Solution 0.5% was chosen as the active control because it has previously been proven to be effective for the reduction of elevated IOP in patients with glaucoma or OHT and is approved for these indications.

IOP will be measured at 08:00, 10:00 and 16:00 ( $\pm 60$  min). At these scheduled visits, BCVA and slit-lamp biomicroscopy will be performed just prior to the 08:00 IOP measurement. Ophthalmoscopy (fundus examination) will be performed after the 16:00 IOP measurement. Vital signs (resting blood pressure and pulse rate) will be collected in sitting position anytime at Visit 1, and approximately 08:00 for Visits 2, and 5 before the morning dose.

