**7.4.4. Visit 3 (Week 1, Day 8 ±2)**

- Update concomitant medications and procedures/therapies.
- An authorized unmasked study staff member, other than the Investigator or Examiner should query the subject regarding dosing compliance and ensure subject has sufficient study medication to complete dosing through Visit 4.
- Query the subject regarding AEs.
- As per Schedule of Events and Procedures [Table 3](#) (for adult subjects) **or** [Table 4 \(for pediatric subjects\)](#), perform the following procedures or assessments immediately before the 08:00 IOP measurement (all ophthalmic procedures to be performed in both eyes):
  - BCVA (before the 08:00 IOP measurement)
    - If more than 10 letters in BCVA were lost compared to the screening visit, then refraction should be performed again.
  - Biomicroscopy (before the 08:00 IOP measurement)
- Perform IOP measurement at 08:00 ( $\pm 60$  min).
- Instill study medication/eye drop after the 08:00 IOP measurement in both eyes (for pediatric subjects, the investigator may elect to dose only one eye). An authorized unmasked study staff should make sure the instillation is performed.
- Perform IOP measurement at 10:00, and 16:00 ( $\pm 60$  min).
- If the subject provided written consent to provide a blood sample for a future pharmacogenomics/genomics laboratory research study, collect the sample at this visit or subsequent visit prior to exit from the study.
  - Note: If a blood sample cannot be collected at this visit, it may be collected at any one of the following Visits, for example, Visits 4, 5 or unscheduled or early termination visit, the subject has provided written consent prior to collection of the sample.
- Schedule the subject to return on Day 43±3 for Visit 4 (Week 6).
- Remind the subject to continue dosing according to the written instructions.
- Inform the subjects they will be reminded of the evening instillation of the study medication by phone call a few days before Visit 4.
- Remind the subjects that the morning dose of Visit 4 will be done at the clinic.
- Remind the subject to bring all used and unused study medication at Visit 4.

[figure not shown]

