4.4. Safety-Related Definitions

4.4.1. Adverse Event

Under Protocol 011710IN, an AE is defined as any untoward medical occurrence that occurs in a study subject, regardless of the causal relationship with the study treatment. An *on-study* AE can occur any time after the date of informed consent through the last study visit. An AE will be considered as *treatment-emergent* if the onset date of the AE occurred on or after the treatment start date till up to 2 days (twice the scheduled dosing interval) after treatment end date.

Treatment-emergent AEs (TEAEs) are a subset of on-study AEs. Both on-study and TEAEs will be collected, but only TEAEs will be tabulated.

The severity of each AE will be graded by the Clinical Investigator as Mild, Moderate, or Severe. AEs will also be rated by the Investigator as to their causality/relationship to the study drug.

Each AE will be classified into a system organ class (SOC) and coded to a preferred term (PT) using Medical Dictionary for Regulatory Activities (MedDRA), version 21.1 published in 2018.

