7.7. Exposure to Study Medication

The duration of exposure to a study medication is measured by days on treatment as derived in [Section 4.1.6](#). For subjects in the Safety Population, the duration of exposure will be summarized using descriptive statistics, and frequency and percentage of subjects will be tabulated by duration category (1-30 days, 31-60 days, or ≥ 61 days) by actual treatment received.

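### With no last-dose date and no Exit Visit, SAP 4.1.3 can end treatment before a known dose or before the first one, and closes the TEAE window one day after the last visit

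*SAP*

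**What the plan says.** SAP 4.1.2 and 4.1.3 define the two dates by actual dosing: "Treatment start date is the date at which a randomized subject takes the first dose of the study medication" and "Treatment end date is the date at which a randomized subject takes the last dose of the study medication". When the last-dose date is missing, SAP 4.1.3 falls back on visits. Completers get the day before Visit 5, and non-completers get the day before the Exit Visit. If there is no Exit Visit date, "then the day before the last available visit date will be considered the treatment end date".

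The end date feeds two safety derivations:
- Exposure (SAP 4.1.6) is end date minus start date plus one. In SAP 7.7 it is "tabulated by duration category (1-30 days, 31-60 days, or ≥ 61 days").
- An AE is treatment-emergent from the start date "till up to 2 days (twice the scheduled dosing interval) after treatment end date" (SAP 4.4.1). The same section restricts the tables to treatment-emergent events.

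The protocol fixes when drops are taken around visits. Section 7.1 puts the first dose at 20:00 on the baseline day: "At Visit 2 (Baseline), subjects will receive their first dose of study medication (study eye drops"). At later visits, "subjects will receive their morning dose of study medication/eye drops following the 08:00 IOP measurement at the investigative site". Section 7.4.4 adds "An authorized unmasked study staff should make sure the instillation is performed", and 7.4.5 and 7.4.6 repeat this. Subjects also leave with drug in hand: kits are dispensed at Visits 2 and 4 (Protocol 10.2), and at Visit 3 staff check that the supply lasts to Visit 4 (7.4.4).

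**The concern.** The fallback contradicts the SAP's own definition of the end date. For a subject still on drug, the last visit at Visit 3 or 4 is itself a dosing day, with the drop instilled under staff supervision. A date one day earlier cannot be the date of the last dose. If the last visit was Visit 2, the fallback date precedes the start of treatment.

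The fallback also takes no account of dosing at home after the last visit. A subject may leave between visits without an exit examination and later report an AE by telephone. That AE can then fall outside the treatment-emergent window although the subject was still taking the drops. Elsewhere unknown dates are handled the other way: SAP Table 5 counts an AE with a completely missing onset date as treatment-emergent, and Protocol 14.5 asks for conservative imputation of AE dates.

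At stake are exposure that is slightly wrong or impossible for some subjects, and AE tables that could omit a few events occurring on drug.

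**Working it through.** The plan gives no figure to reproduce here; the check is date arithmetic on its own rules.

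Inputs:
- Last available visit on study day V. The target days are 1, 8 and 43 for Visits 2, 3 and 4, and 91 for Visit 5 (schedule in Protocol 7.4).
- Treatment start on Day 1, the evening of Visit 2 (Protocol 7.1).
- Imputed end date = V − 1 (SAP 4.1.3).
- Exposure = end − start + 1 (SAP 4.1.6).
- Last TEAE day = end + 2 = V + 1 (SAP 4.4.1).

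The last column below is a ceiling. It assumes that the subject kept dosing up to the target day of the next kit visit (Day 43 or Day 91). The documents do not show this, and the true number runs from 0 up to that ceiling.

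| Last visit (V) | Imputed end | Exposure | SAP 7.7 category | Last TEAE day | Dosing days outside window, at most |
|---|---|---|---|---|---|
| Visit 2 (1) | day before Day 1 | (D − 1) − D + 1 = 0 | none | Day 2 | 43 − 2 = 41 |
| Visit 3 (8) | Day 7 | 7 − 1 + 1 = 7 | 1–30 | Day 9 | 43 − 9 = 34 |
| Visit 4 (43) | Day 42 | 42 − 1 + 1 = 42 | 31–60 | Day 44 | 91 − 44 = 47 |

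D is the calendar date of the first dose.

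If the end date is moved to the visit date, exposure becomes 1, 8 and 43 days and the last TEAE day becomes Day 3, 10 and 45. Dating the end before the on-site dose therefore costs exactly one day of exposure and one day of window. The rest of the gap comes from possible dosing at home after the visit, which changing the end date to the visit date does not recover.

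Which AEs are affected: any AE with onset from the first dose to day V + 1 is treatment-emergent under the rule as written, including one starting on the day of the supervised dose. Only an AE with onset at V + 2 or later is lost to the tables, and it must be learned outside a visit, because V is the last visit. Protocol 12.1.1.1 has AEs sought at every contact, and 12.1.1.2 has them recorded until withdrawal or the exit visit, so such reports can enter the database.

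**The case against.** The strongest case against is that the conditions rarely coincide. The subject must be a non-completer with no Exit Visit date and no last-dose date, and the AE must start at V + 2 or later and be reported outside a visit. Protocol 8.5 illustrates loss to follow-up as the case where contact cannot be made, and such a subject would yield few later AEs. Where contact is made, Protocol 12.1.1.2 asks for the action taken with study medication for each AE, so the call might also supply a last-dose date. For a subject last seen at Visit 2, evidence that the first drop was taken at home may likewise say something about the last one. This stands as an argument that few subjects are affected. It does not make the imputed date right when the rule applies, and withdrawal by telephone remains a realistic route to it.

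A reader might infer three stronger points, which the documents do not support:
- *AEs in subjects lost to follow-up generally stop being treatment-emergent.* The two-day tail keeps every post-dose AE with onset through the day after the last visit.
- *The rule always predates a supervised dose and always understates exposure.* Protocol 7.4.6 and 8.5 encourage subjects who stop drug to keep attending for observation. If such a visit is the last one, the imputed date may fall after the true last dose.
- *A safety signal is hidden or the arms are biased.* SAP 9.1 lists non-TEAEs, SAEs, AEs leading to drug discontinuation and ESIs. The rule is the same in both arms, SAP 6 excludes testing of safety measures, and nothing shows a difference between arms.

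**Conclusion.** The fallback is wrong as written, with a small expected effect. For a subject still on drug at Visit 3 or 4, it misdates the end of treatment by at least one day. For a dosed subject last seen at Visit 2, it gives an end date before the start and an exposure of 0 days that cannot be tabulated.

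The AE consequence is limited to onsets two or more days after the last visit, which are listed but not tabulated even if the subject was still dosing. The ceilings of 41, 34 and 47 days rest on on-target visits and dosing up to the next kit visit. The number of subjects is not given and is probably small. Severity is low.

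**What to change.** In SAP 4.1.3, for a non-completer with no last-dose date and no Exit Visit date, set the treatment end date to the latest date with documented dosing. That is the last visit date if the on-site dose was given, or the date of a later contact at which the subject reported dosing. Add a floor so that the end date is never earlier than the treatment start date.

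In SAP 4.4.1, add that when the last-dose date is unknown and the subject is not known to have stopped study drug, AEs with onset up to the last contact count as treatment-emergent, in line with Table 5. Exclude subjects in off-drug observational follow-up, so that events long after stopping are not attributed to treatment.

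For completers, the protocol first needs reconciling. The synopsis paragraph following the Comparator description has dosing run to the morning before Visit 5, whereas 7.4.6 has a drop instilled at Visit 5. Once that is settled, align the completer rule with it, and check the Exit Visit rule too, since the schedule puts Visit 5 and early termination in one column.

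The cost is a few lines of SAP text and one derivation, with no change to study conduct. The downside is that a few AEs after an undocumented stop may be counted as treatment-emergent.

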4.1.4. Study Day

The *study day* describes the relative day of an observation starting with the reference date designated as Study Day 1. In this study, the treatment start date is the reference date. Thus, the study day will be calculated as:

- For days prior to the treatment start date, Study Day = Date – Treatment Start Date
- For days on/after the treatment start date, Study Day = Date – Treatment Start Date + 1

4.1.5. Out-of-Window Measurements, Analysis Visit, and Analysis Window

Analysis visit is a timing variable to be used for analyses involving visits. For each analysis visit, an *analysis window* is set up to determine the analysis visit to which a measurement should be mapped ([Table 2](#)).

The analysis visit of a measurement will be determined based on the study day of the measurement and specified analysis windows and is not necessarily the same as the study visit at which the measurement was collected. For example, an out-of-window measurement collected at the Week 1 study visit will be mapped to the Week 6 analysis visit, if the study day of the measurement falls into the analysis window of Week 6.

Table 2: Analysis Visit and Analysis Window

Analysis Visit Name (Target Day)	Protocol Visit Window	Analysis Window	
		Ophthalmoscopy, Iris Color, Eyelash, and Eyelid	Other Parameters
Baseline (Day 1)	[1, 1]	- 1]	- 1]
Week 1 (Day 8)	[6, 10]	NA*	[2, 22]
Week 6 (Day 43)	[40, 46]	NA*	[23, 61]
Month 3 (Day 91)	[84, 98]	[2 -	[62 -

*Not collected at this visit.

If there are two or more visits that fall into the same analysis window, then the visit closest to the target assessment day will be selected for that visit window. In the case that two visits are equidistant to the target assessment day, i.e., one is before and one is after the target assessment day, the later one will be selected for that visit.

For analyses of IOP involving post-baseline visits, if there are two or more visits that fall into the same analysis window of a post-baseline visit, then the visit in which IOP are measured at all the scheduled timepoints (8:00, 10:00, and 16:00) will be selected for that analysis visit first, before applying the above rule.

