**Note:**

- **If the study drug administration is discontinued prior to Visit 5, the subject should be encouraged to still participate in follow-up study visits until Visit 5 on an observational basis.**
- **If the study drug administration is discontinued prior to Visit 5, then to the extent possible, all procedures for Study Exit/Early Termination as per [Table 3](#) (for adult subjects) or [Table 4](#) (for pediatric subjects) will be performed on the day of early termination. Subjects who are discontinued from the study early will not be replaced.**

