## 8.5. Subject Withdrawal Criteria

An early termination occurs when a subject who provides written informed consent ceases participation in the study, regardless of circumstances, before the completion of the study. Subjects may be voluntarily discontinued from study medication or withdrawn from the study at any time for any reason. In addition, the Principal Investigator or Medical Monitor may discontinue the study drug administration or terminate a subject's study participation due to any of the following reasons:

- AE (e.g., not compatible with study continuation)
- Non-compliance with study drug
- Lack of efficacy (e.g., IOP exceeds 34 mmHg in either eye after randomization)
- Progressive disease
- Protocol deviation (e.g., not fulfilling eligibility criteria)
- Pregnancy
- Voluntary withdrawal by subject at any time for any reason
- Lost to follow-up (e.g., no contact is possible)
- Death
- Other

If the study drug administration is discontinued prior to Visit 5, they should be encouraged to still participate in all follow-up study visits until Visit 5 on an observational basis.

[figure not shown]
If the study drug administration is discontinued prior to Visit 5, then to the extent possible, all procedures for Early Termination will be performed on the day of early drug discontinuation as per [Table 3](#) (for adult subjects) or [Table 4](#) (for pediatric subjects). Subjects who are discontinued from the study early will not be replaced.

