9.4. Ophthalmoscopy

Cup-to-disc ratio will be summarized with n, mean, standard deviation, median, minimum and maximum by treatment and analysis visit for study eyes and fellow eyes separately. In addition, subjects with at least 0.2 increase in cup/disc ratio from baseline will be listed.

Glaucomatous optic nerve findings will be assessed as 0 = none, 1 = mild, 2 = moderate, or 3 = severe. Frequency and percentage of rating scores will be summarized by treatment and analysis visit for study eyes and fellow eyes, separately. In addition, subjects with any worsening (increase) of ≥ 2 units from baseline will be listed.

Retina/Macula/Choroid and vitreous will be assessed as normal or abnormal. Shift from baseline at Month 3 will be summarized by treatment on study eyes and fellow eyes separately. In addition, subjects with change from baseline from normal to abnormal in these parameters will be listed.

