9.5. Eyelid Sulcus, Eyelid, Eyelash, and Iris Color

For changes from baseline in eyelid pigmentation, eyelid hair growth, eyelash length, eyelash thickness, eyelash pigmentation, eyelash number, and iris color/pigmentation, frequency and percentage of subjects with No change, Increased, or Decreased will be summarized by treatment and analysis visit for study eyes and for fellow eyes. For changes from baseline in eyelid sulcus, count and percentage of changes (Yes) will be summarized by treatment and analysis visit (Month 3) for study eyes and for fellow eyes. In addition, any changes from baseline in eyelid sulcus will be listed.

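### Month 3 fundus and iris/eyelash/eyelid tables can replace an on-drug exit examination with an off-drug Visit 5 one, and no on-treatment summary is planned

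*SAP*

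**What the plan says.** SAP 4.1.5, Table 2, has a separate window column headed "Ophthalmoscopy, Iris Color, Eyelash, and Eyelid". In that column Week 1 and Week 6 are marked as not collected, and everything from Day 2 onward maps to Month 3, whose target is Day 91 and whose protocol visit window is Days 84 to 98. If several visits share a window, "the visit closest to the target assessment day will be selected for that visit window"; when two are equally distant, "the later one will be selected for that visit". The one exception is introduced by "For analyses of IOP involving post-baseline visits" and prefers visits with all three pressure readings. It does not concern drug status.

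Protocol 8.5 says that, where feasible, "all procedures for Early Termination will be performed on the day of early drug discontinuation". The note closing Protocol 7.4.6 adds that "the subject should be encouraged to still participate in follow-up study visits until Visit 5 on an observational basis". Ophthalmoscopy and the iris/eyelash/eyelid assessment are both due at Visit 5/exit (Protocol Table 3, 21.3.4 and 21.3.12).

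The results feed SAP 9.4, where for retina/macula/choroid and vitreous "Shift from baseline at Month 3 will be summarized by treatment on study eyes and fellow eyes separately", and SAP 9.5, where for the eyelid sulcus "count and percentage of changes (Yes) will be summarized by treatment and analysis visit (Month 3) for study eyes and for fellow eyes". SAP 9 presents all safety measures by treatment actually received.

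**The concern.** A subject who stops drug early but stays in the study can contribute two examinations to one window: one on the stop day and one at Visit 5, weeks after the last dose. Selecting on calendar distance from Day 91 favours the second. The table then reports, under a drug arm, an eye that may have been unexposed for most of the study.

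This matters most for findings that can recede once drug is withdrawn. Protocol 12.1.3 names macular edema as having been reported in DE-117 trials, and SAP 9.1.3 gives cosmetic lid, lash and iris changes their own summary. A subject who stops because of an ocular problem is plausibly the one whose stop-day examination differs from the Month 3 examination. If the finding has resolved, the by-arm examination table records nothing, and it may disagree with the adverse event tables for the same subject. If it has not resolved, on-drug and off-drug status still share one Month 3 label.

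**Working it through.** The plan states no figure on this point, so there is none to reproduce. The check applies the selection rule to every relevant pair of examination days.

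**Inputs.** Window start Day 2, target Day 91, nearest visit kept, ties to the later visit (SAP 4.1.5). Visit 5 on day v, from 84 to 98 (Protocol Table 3; SAP Table 2). Stop-day examination on day d, from 2 to 90, with v > d (Protocol 8.5).

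**Step 1: when Visit 5 must win.** Visit 5 is kept if |v − 91| ≤ 91 − d, because a tie goes to the later visit. The largest in-window distance is 98 − 91 = 7. So Visit 5 is kept for every in-window v whenever 91 − d ≥ 7, that is, d ≤ 84. Day 84 against Day 98 is a 7–7 tie and goes to Day 98.

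**Step 2: when the stop-day examination survives.** For d = 85 to 90 it is kept only if v − 91 > 91 − d, that is, v > 182 − d. The number of in-window days meeting this is 98 − (182 − d) = d − 84, giving 1 + 2 + 3 + 4 + 5 + 6 = 21 pairs.

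**Step 3: all pairs.** Stops on Days 2 to 83 give 82 × 15 = 1230 pairs. Stops on Days 84 to 90 give 14 + 13 + 12 + 11 + 10 + 9 + 8 = 77. The total is 1307, and Visit 5 is selected in 1307 − 21 = 1286, or 98.4%. This is a share of day pairs, not of subjects.

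**Step 4: late or missed Visit 5.** The condition v > 182 − d also covers late visits. A Day 75 stop keeps its stop-day examination only if Visit 5 falls after Day 107 or is not done.

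**Step 5: time off drug in the retained value**, with Visit 5 on Day 91 and last dose on the stop day (91 − d):

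| Stop day | Days off drug at Visit 5 |
|---|---|
| 10 | 81 |
| 43 | 48 |
| 75 | 16 |
| 84 | 7 |

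**Step 6: does anything else in the SAP restore the on-drug value?** SAP 6.2.2 uses observed safety data without an on-treatment restriction. The limit of 2 days after treatment end (SAP 4.4.1) applies to adverse events only. Censoring after rescue (SAP 6.2.1 and 8) applies to IOP only. SAP 9.4 and 9.5 contain no last-on-treatment or worst-value table. SAP 7.1 does expect these subjects, since it counts those who stopped drug early but remained in the study.

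**Step 7: what is captured elsewhere.** Adverse events, including those leading to drug discontinuation, are tabulated by arm (SAP 9.1), with further summaries for ocular inflammation, macular edema and cosmetic changes (9.1.1 to 9.1.3). SAP 9.4 lists normal-to-abnormal fundus changes, cup-to-disc increases of at least 0.2 and optic-nerve worsening of at least 2 units; 9.5 lists eyelid sulcus changes. None of these listings is said to be confined to the selected visit. Not covered by a listing are one-unit optic-nerve worsening and eyelid pigmentation, eyelid hair, eyelash and iris changes. If these are not reported as events, the Month 3 table is their only planned output.

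**The case against.** The strongest reply is that the important signals travel by another route. Any macular edema must be reported as an event of special interest within 24 hours and followed up (Protocol 12.1.3 and 12.1.4). SAP 9.1.2 summarizes its onset, duration and acuity change. An event found on the stop day lies inside the treatment-emergent period. A reader might infer that the selection rule hides macular edema or removes cosmetic effects from the by-arm results; the documents do not support that for findings recorded as adverse events. This part of the objection stands and confines the point mainly to examination findings not so recorded.

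Other stronger readings also fail:

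- That every early stopper is affected. The stop-day examination is required only where feasible, and continued attendance is only encouraged. SAP 3.4 ties the exit assessments to leaving the study, so under its wording a subject who stays may have no stop-day examination to displace. The attended Month 3 value is still off drug.
- That Visit 5 always wins. Stops on Days 85 to 90, or a late Visit 5, can reverse the choice.
- That harm is necessarily understated. This requires a finding present at stop and gone by Visit 5. The documents give no recovery data, and Protocol 12.1.4 allows for irreversible or stable outcomes.
- That the window has no upper limit. Symbols appear to be lost from the printed table. The argument needs only the Day 2 start.

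These summaries are also descriptive and untested (SAP 6), so no confirmatory conclusion depends on them. None of this supplies an on-treatment view of the examinations: no provision gives the on-drug examination priority or marks the off-drug one.

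**Conclusion.** The point holds within limits. Where both examinations exist and Visit 5 is in window, the off-drug one is retained for every stop through Day 84. The Month 3 tables by actual treatment then mix exposed and unexposed status and can understate reversible findings, chiefly those not reported as adverse events. Unscheduled ophthalmoscopy, which is optional, would normally lose to Visit 5 in the same way.

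The number affected cannot be derived, because the documents give no discontinuation rate. For scale only, if 5% to 10% of the planned 200 per arm stopped and stayed (an assumption), 200 × 0.05 = 10 to 200 × 0.10 = 20 subjects per arm would carry an off-drug Month 3 value. Only those abnormal at stop and recovered by Visit 5 would change a table, so the effect on counts would be smaller. Any difference between arms depends on discontinuation and recovery patterns that are not stated.

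**What to change.** In SAP 4.1.5, 9.4 and 9.5:

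- Keep the Month 3 summary, and flag or tabulate separately the Month 3 examinations done off drug.
- Add a by-arm last-on-treatment summary for ophthalmoscopy and iris/eyelash/eyelid assessments, using the last examination up to a stated limit after the last dose. The 2-day limit already used for treatment-emergent events is one option.
- Optionally add a worst-post-baseline table as supportive, noting that unscheduled examinations may differ in frequency between arms and so bring an ascertainment bias of their own.

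Two inconsistencies need reconciling. SAP 3.4 attaches exit assessments to leaving the study, while Protocol 8.5 attaches them to stopping drug. SAP Table 4 describes lid, lash and iris changes as assessed at every follow-up visit, while Table 2 marks them as not collected at Week 1 and Week 6. If they were collected then, those on-drug assessments would fall in the same window and normally lose to Visit 5.

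The cost is SAP wording and a few descriptive tables from data already collected; no visit, procedure or sample size changes. The downside is that the safety tables may look slightly less favourable.
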